Ketamine, given for postoperative pain control, can be hypothesized to have long lasting analgesic effects as well as effects on improving mood and function in the postoperative period. Ketamine can be administered as a single dose in the post-anesthetic care unit (PACU), where patients are closely monitored for potential side effects. We hypothesize that postoperative use of ketamine should lead to improvement in pain indices including visual analog scale (VAS), a decrease in opioid requirement, mood improvements as measured by psychometric indices, and finally improvements in functional measures including early mobility and faster discharge from the hospital. In addition, we will assess serum levels of IL-1, 6, TNF- α , and BDNF to see if alterations in levels of cytokines and neurotrophic factors occur with postoperative pain and how ketamine treatment may influence the levels of these biomarkers.

Study Objective

Specific aim 1: examine the effect of a single, subanesthetic dose (0.4mg/kg) of ketamine vs. saline control on mood and postoperative function in patients who have undergone gastric bypass and sleeve gastrectomies.

Pain relief and changes in postoperative mood and function will be assessed using both patient report, in the forms of a series of questionnaires, and medical chart review. The questionnaires we use will be Beck Depression Inventory (BDI), Visual Analog Scale (VAS), McGill's short form, QoR-15 form and the Montgomery-Asberg Depression Rating Scale (MADRS). Please see below for a detailed discussion of these forms. In addition, from the chart review we will monitor length of stay during hospitalization, opioid usage per hour during the PACU stay before and after ketamine infusion, total opioid usage per day throughout the hospital stay, time to out of bed to chair, and spirometry use after ketamine infusion.

Specific aim 2: examine the effect of a single, subanesthetic dose (0.4mg/kg) of ketamine vs. saline control on inflammatory cytokines and neurotrophic factors in the postoperative period.

We will examine the effect of ketamine on proinflammatory markers and neurotrophic factors known to be linked with pain. We will examine levels of interleukin factor 1 and 6 (IL-1, IL-6), TNF- α , and BDNF. This aim will provide potential mechanism of action for ketamine.

Overall study design and plan

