An additional component of the study, which is entirely optional, is to obtain patient serum samples (about two teaspoons) in the operating room and 15 minutes and 4 hours after ketamine infusion. We will use these samples to assess levels of IL-1, IL-6, TNF- α , and BDNF, which are markers for pain. In addition, with patient consent, we will also store serum samples for future research use to measure other cytokines and neurotrophic factors and molecular markers associated with pain and depression.

Study site: Tisch Hospital

Outcome measures

Primary outcome measure: scores on the following questionnaires: 1) The Beck Depression Inventory (BDI); 2) Visual Analog Scale (VAS) score; 3) McGill's short form; 4) QoR-15 form; and 5) Montgomery-Asberg Depression Rating Scale (MADRS). The BDI and MADRS provide assessments for mood and function, VAS and McGill's assess pain, and QoR-15 assesses patient's overall satisfaction with postoperative recovery.

After consent is achieved in the pre-admission clinic prior to surgery, patients will be asked to fill out BDI, MADRS and QoR-15 forms to establish baseline scores. The BDI, MADRS will be filled out on postoperative days (POD) 0 after the infusion of ketamine, and BDI, MADRS and QoR-15 forms will be repeated on POD1, 2 and 7. McGill's short form will be filled out prior to discharge from the PACU and on POD 1, 2 and 7. VAS will be filled prior to PACU discharge, and every day while patient is in the hospital and on POD 7. VAS is a routine part of hospital care and will be administered daily whether a patient is enrolled in the study or not. If a patient has been discharged prior to POD2 or 7 (patients typically are discharged on POD2 or 3 in our practice), then a member of the study team will contact the patient by telephone to fill out these questionnaires.

Secondary outcome measures: 1) length of stay during hospitalization; 2) opioid usage per hour during the PACU stay before and after ketamine infusion; 3) opioid usage per day throughout the hospital stay; 4) time to out of bed to chair (OOB); 5) spirometry use 4 hours after the termination of ketamine infusion; 5) anti-emetic use in the PACU.

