Length of stay, opioid usage, and anti-emetic use will be recorded from electronic medical chart. Patient will be asked to record and report the time to OOB. Spirometry use will be assessed by a study team member to determine whether the patient is meeting the goal set by the surgical team 4 hours after ketamine infusion.

Exploratory secondary outcome measures: changes in serum levels of IL-1, IL6, TNF- α , and BDNF, which will be collected at baseline (in the OR preoperatively), and 15 min and 4 hours after the termination of ketamine infusion.

Study population

Inclusion criteria:

1. Adults, >18 years, <65 years, who will undergo gastric bypass or sleeve gastrectomy.
2. Subject is non-lactating and is either:
 - a. Not of childbearing potential; or
 - b. Of childbearing potential but is not pregnant at time of baseline as determined by pre-operative pregnancy testing.
3. Subject is ASA physical status 1, 2, or 3.
4. Subject who is deemed medically stable

Exclusion criteria:

1. <18 years of age; >65 years of age
2. Pregnant or breastfeeding
3. Does not speak or understand English (the study forms used are copy-right in English)
4. Cognitively impairment (by history) or clinical signs of altered mental status
5. History of misuse or abuse of ketamine
6. History of chest pain or chest pain in the PACU
7. Use of a medication that interferes with metabolism of ketamine within the last 24 hours
8. A diagnosis of schizophrenia and/ or a history of chronic antipsychotic medication use
9. History of head trauma
10. History of intracranial mass or hemorrhage
11. History of stroke
12. History of cardiac arrhythmia
13. Subject for whom ketamine is contraindicated
14. Unwillingness to give informed consent according to HIC guidelines

Entry into Study

Flyers will be designed and posted in the bariatric clinic as well as the pre-admissions testing (PAT) clinic to inform patients about this study. Patients will be recruited from the bariatric clinic during their visit with the pre-surgical clinic visit with their surgeons, from the PAT during their preadmission visit, or from the holding area on the day of surgery. Researchers will hold a general discussion with interested patients regarding the study. The patient may have family included, if he/she prefers. We will be approaching all subjects (male and female) who are undergoing laparoscopic gastric bypass or sleeve gastrectomy.

Pre-Study Screening

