The Pharmacy at Tisch Hospital will randomize and prepare samples (study medication or saline control). Study medications and placebo will be kept by the Pharmacy staff at Tisch Hospital until use.

Main Study

Pharmacologic profile of study drug

Ketamine [(+/-)-2-(2-chlorophenyl)-2-(methylamino)-cyclohexanone] is a white, crystalline powder or clear liquid. It is a schedule III substance and is classified as a dissociative anesthetic. Ketamine is available as a racemic mixture with the S-(+)- isomer being more potent than the R-(-)- isomer. It is commercially supplied as the hydrochloride salt in 0.5 mg/mL and 5 mg/mL ketamine base equivalents. Clinically, it is commonly used as an anesthetic induction agent for diagnostic and surgical procedures prior to the administration of general anesthetics. It is also used as a low dose infusion for analgesia. For induction of 5-10 minutes surgical anesthesia, a dose of 1.0-4.5 mg/kg is intravenously administered; 6.5-13 mg/kg is given intramuscularly for 12-25 minutes of surgical anesthesia. As an analgesic, it is infused at a rate of 0.1 - 0.5 mg/kg/hr, with or without a loading dose.

The risks for ketamine are well studied. In general, ketamine is a well-tolerated medication. However, the following risks have been reported.

Pharmacokinetics: Bioavailability following an intramuscular dose is 93%, intranasal dose 25-50%, and oral dose 20±7%. Ketamine is rapidly distributed into brain and other highly perfused tissues, and is 12% bound in plasma. The plasma half-life is 2.3 ± 0.5 hours. Oral administration produces lower peak concentrations of ketamine, but increased amounts of the metabolites norketamine and dehydronorketamine. Ketamine and its metabolites undergo hydroxylation and conjugation. Norketamine produces effects similar to those of ketamine. There are no significant differences between the pharmacokinetic properties of the S-(+) and R-(-)-isomers.

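### No pain score is tied to any serum draw, so the exploratory question whether cytokines and BDNF change with postoperative pain would rest on mistimed pairs

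*Combined protocol and SAP*

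**What the plan says.** **The question.** The Study Rationale says serum IL-1, IL-6, TNF-α and BDNF will be measured "to see if alterations in levels of cytokines and neurotrophic factors occur with postoperative pain", and also to see how ketamine influences them. Specific aim 2 is narrower: ketamine versus saline on the markers.

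**The blood draws.** Under Outcome measures, the exploratory secondary outcome is change in serum levels, "which will be collected at baseline (in the OR preoperatively), and 15 min and 4 hours after the termination of ketamine infusion". The section on overall study design makes sampling optional.

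**The pain scores** (also Outcome measures). "VAS will be filled prior to PACU discharge, and every day while patient is in the hospital and on POD 7". "McGill's short form will be filled out prior to discharge from the PACU and on POD 1, 2 and 7". At baseline, "patients will be asked to fill out BDI, MADRS and QoR-15 forms to establish baseline scores"; neither pain instrument is on that list. On the day of surgery, "The BDI, MADRS will be filled out on postoperative days (POD) 0 after the infusion of ketamine". Those two are mood scales and are not timed to the draws either.

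**The analysis.** The Statistical Analysis text, which appears twice (once on its own and once within the Data Safety and Monitoring Plan), names Pearson and Spearman correlation in general terms. It mentions neither the markers nor pain, and it gives no rule for pairing a blood sample with a score.

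**The concern.** Relating a marker to pain requires the two to be measured at about the same time. Postoperative pain can change within hours, and the protocol leaves other analgesics unrestricted, so a score from another time describes the pain at the draw only imperfectly. Pairing it with the sample would tend to pull the association towards zero.

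The pre- to post-operative change in a marker is no substitute. Every patient has surgery and anesthesia between the first draw and the two later ones, so a mean change cannot be assigned to pain. The between-patient association is what bears on the stated question, and it needs a score at the draw.

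A score that was not taken cannot be recovered later. The protocol also stores consenting patients' serum for future work on markers of pain and depression, and that work would inherit the same gap.

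**Working it through.** **1. The plan's own figure.** The only sample-size calculation concerns the psychometric outcome: difference 22.5%, SD 40%, power 0.8, alpha 0.05 (taken as two-sided).

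n per arm = 2 × (1.960 + 0.842)² × (40/22.5)² = 2 × 7.85 × 3.16 = 49.6, rounded up to 50.

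This reproduces the stated 50 per arm (power 0.803 at n = 50). It does not involve the markers and is untouched by this point. No power target is given for the markers.

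**2. The two schedules side by side.**

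| Serum draw | Pain score specified at that time | Nearest pain score in the plan |
|---|---|---|
| Pre-operative, in the OR | None | None before surgery |
| 15 min after end of infusion | None | VAS and McGill before PACU discharge, at an unfixed time |
| 4 h after end of infusion | None | The same PACU scores, or those of the next day |

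None of the three draws has a specified concurrent score. The infusion is given in the PACU, so the PACU score could lie close to the 15-minute draw. The documents do not say how long patients stay in the PACU after the infusion, so the gap cannot be calculated. One PACU score cannot be concurrent with both the 15-minute and the 4-hour draw.

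**3. What mistiming could cost (illustration).** The documents give no marker-pain correlation and no correlation between pain scores at different times, so both are assumed:

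- true same-time correlation ρ = 0.4, with 0.3 as a check;
- a mistiming factor a of 0.9, 0.7 or 0.5, so that the observable correlation is r = a × ρ. This holds if the available score relates to the marker only through pain at the draw;
- n = 100 if everyone gives blood, or 50 if half do (an assumption, since sampling is optional).

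Power (Fisher z, two-sided 0.05) = Φ(atanh(r) × √(n − 3) − 1.960).

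Example with ρ = 0.4, a = 0.5, n = 100: r = 0.20, atanh(r) = 0.2027, √97 = 9.849. The product is 1.997; subtracting 1.960 leaves 0.037, and Φ(0.037) = 0.51.

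| ρ | n | same-time | a = 0.9 | a = 0.7 | a = 0.5 |
|---|---|---|---|---|---|
| 0.4 | 100 | 0.99 | 0.96 | 0.81 | 0.51 |
| 0.4 | 50 | 0.83 | 0.73 | 0.50 | 0.28 |
| 0.3 | 100 | 0.86 | 0.78 | 0.56 | 0.32 |
| 0.3 | 50 | 0.56 | 0.48 | 0.31 | 0.18 |

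Mild mistiming costs little at n = 100. Strong mistiming, or partial uptake of sampling, costs a good deal.

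**The case against.** The strongest reply is that the trial never commits to a marker-pain correlation. Specific aim 2 compares arms, the exploratory outcome is change in levels, and the Pearson/Spearman sentence is generic. That stands. A reader might infer that such correlations are already planned, but the documents do not say so. What they do contain is the question in the Study Rationale, with no data collection matched to it. One could read that question as simple change from before to after surgery, which the three draws do measure; but that reading cannot separate pain from surgery and anesthesia.

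Second, the PACU score may be close enough to the 15-minute draw. This may be so for some patients. The supportable statement is that its timing is not fixed; the clear gaps are at 4 hours and at baseline.

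Third, a reader might argue from the protocol's pharmacokinetics ("The plasma half-life is 2.3 ± 0.5 hours") that a next-day score reflects a different pain state because little drug remains. The documents do not support that step. It says nothing about the placebo arm, it assumes that pain follows plasma level, and the Study Rationale hypothesises long-lasting analgesia.

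Fourth, a same-time score would not isolate pain. Greater surgical injury can raise both pain and cytokines. This is correct and limits what the fix can deliver.

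Finally, the power figures depend on the chosen inputs. They do, and they show direction and possible range only.

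**Conclusion.** The gap is real and its consequence is modest. No pain score is tied to any serum draw, none is scheduled at 4 hours, and none exists at baseline. The randomised comparison of marker levels needs no pain score and remains valid, as does the sample size. What suffers is an optional, exploratory association that the rationale raises.

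With an assumed true correlation of 0.4 and 100 patients sampled, power falls from 0.99 to between 0.96 and 0.51 across the attenuation factors considered. The actual loss is unknown, because neither the correlations nor the timing of PACU discharge is given. A reader might conclude that the marker question is lost altogether. The documents do not support that, since some PACU scores may fall near the first post-infusion draw. The point is a cheap improvement to make before data are collected, not a threat to the trial's main results.

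**What to change.** - **Outcome measures, and the description of serum sampling in the overall design section:** record a VAS and the clock time at each draw (pre-operative, 15 minutes, 4 hours). The documents do not say whether the OR draw precedes induction; if it does not, the baseline VAS should be taken just before induction.
- **Statistical Analysis (both copies):** state that marker-pain associations use these same-time pairs, adjusted for treatment arm and time point and allowing for repeated samples from one patient. Without adjustment for arm, a pooled correlation could simply reflect ketamine moving both quantities. State also that the associations are exploratory and do not fully separate pain from surgical injury.

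**Cost.** A few seconds of rating and one CRF field per draw, at times when blood is already being taken. At 4 hours a contact already exists: "Spirometry use will be assessed by a study team member". The documents do not say who draws the blood or who is present at 15 minutes, so that assignment should be written down. No treatment, care or other endpoint changes.

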Randomized, double-blind, placebo controlled study on the effect of a single postoperative administration of low dose ketamine after gastric bypass and gastrectomy surgeries

Primary Investigator: [name]. Ph.D.

New York University Langone Medical Center, Department of Anesthesiology

Study Number: S13-00719

Background

Bariatric surgeries for the treatment of obesity and type II diabetes represent one of the most common abdominal operations, with over 300,000 cases performed in 2011.¹ Postoperative care is a critical component for outcome from these procedures. Optimal postoperative pain management, however, can be difficult to achieve. While many incisions are small, a significant proportion of patients who undergo bypass or sleeve gastrectomy still stay in the hospital for more than two to three days, and patients can suffer from a combination of incisional and visceral pain. Pain control currently is achieved through a combination of opioids, Acetaminophen, and NSAIDs. Opioids are the most powerful analgesic in this group. Opioids, however, are well known to cause sedation and respiratory depression, which can significantly impact respiratory status of bariatric patients, many of whom already suffer from respiratory compromise due to obesity and obstructive sleep apnea. NSAIDs, meanwhile, may increase the rate of bleeding complications. Thus, additional analgesics are needed to achieve optimal pain control.

A key component of postoperative pain experience is depressed mood, which further complicates functional recovery.^{2,3} Bariatric patients, in particular, have a high co-morbidity of depression, which can be worsened by postoperative pain.⁴⁻⁶ Optimal pain control, on the other hand, has been shown to improve patient satisfaction, elevate mood, and allow early participation in physical rehabilitation such as early mobility, all of which contribute to better surgical outcome. Studies are needed, however, to examine additional postoperative measures that can enhance functional recovery in bariatric patients.

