This is a randomized, double-blind, placebo-controlled, two-arm parallel, single-center study. One hundred subjects (50 in each arm) will be enrolled. Subjects, between the ages 18 and 65, undergoing laparoscopic gastric bypass or sleeve gastrectomy under general anesthesia will be screened for eligibility to participate in the study. Subjects will be screened, recruited and consented during the preadmission visit prior to surgery. Eligible subjects will be randomized to one of the two treatment group in a 1:1 ratio to receive either IV ketamine (0.4mg/kg) or matching placebo. Both men and women will be recruited, and there is no limitation as to racial and ethnic origin.

Participation in the study will not alter the patient's surgical or anesthetic care, post-anesthetic care, or care on the floor. In the PACU, patients, if deemed medically stable by the study physician, will receive either 0.4mg/kg IV ketamine or placebo. All patients will also receive standard post-anesthetic monitoring and care, as well as routine care after transfer out of the PACU. There is no restriction on the use of other analgesics throughout the hospital stay. Patients are followed until the date of discharge, and endpoints (see below) are collected from patient reports as well as from medical charts. During their hospital stay (and once after their discharge from the hospital), patients will fill out five questionnaires which provide estimates of their postoperative pain control, mood and function, and quality of postsurgical recovery.

Patients will be randomized using a block randomization code for assigning 100 subjects to two groups. In Excel we generated 100 random numbers. In the next column we inserted multiple copies of the sequence PCPC where p= "placebo" and c = "control", forming 25 blocks. Then we sorted the random numbers in each 4 subject block, including the assignment letters (P, C) in the sort. The remaining list of Ps and Cs is the randomization.

To check the balance, we then did running counts of the cumulative repeats of "p" and "c" and "p - c". The tally for each totaled 50 and the two groups were always within 2 counts of being perfectly balanced, which met our goal. The list can be extended at will to accommodate screening failures.

Randomization lists will be sent to the pharmacy who will then be able to distribute the study drug/placebo as patients are enrolled and undergoing surgery, and the remainder of the study staff will be blinded.

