Potential subjects will have an initial pre-study screening, conducted by a member of the research team, to determine eligibility for the study. Potential subjects who are non-English speaking will be automatically excluded, because the questionnaires are copyrighted in English only. Subjects who do not have the capacity to consent will not be recruited. All other subjects will be recruited. For any patient who might be illiterate, consents will be read to him or her and witnessed by available staff or family member.

Informed Consent

Eligible patients will be assessed for capacity to give informed consent by a study team member. Medical clearance/status/stability will be addressed by members of the research team. Eligible patients will be invited to participate in the study. A verbal explanation of the study will be given followed by a written consent form. Study staff members are experienced at consenting patients for anesthesiology studies, and they include physicians as well as research associates.

[figure not shown]
Intervention Administration

Ketamine bolus doses of 0.4 mg/kg (by ideal body weight) will be prepared and stored by the Pharmacy staff at Tisch Hospital and will be delivered to the PACU on an on-call basis when required for a study subject. The study drug will be administered in accordance to best practices. Ketamine will be given via intravenous infusion through an IV line established in the PACU. All patients will have an IV line in the PACU as per standard postoperative care protocol after bariatric surgery. If necessary, an additional IV line will be placed by the study team for the infusion of the study drug. The study drug or control will be administered over <60 minutes. The dose for ketamine will be fixed at 0.4 mg/kg (ideal body weight). The staff administering the infusion will have no knowledge whether the agent is drug or saline control. The patient will be monitored in the PACU according to the standard PACU protocol. In addition, the patient will be monitored for any potential side effects of the medication, which include hypertension, tachycardia, nystagmus, perceptual disturbances, confusion, sedation, euphoria, dysphoria, and dizziness. These side effects are uncommon, and a majority of these side effects are expected to resolve shortly after infusion.¹³ Side effects will be documented and treated if necessary as per standard PACU protocol.

Study drug storage

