Pharmacodynamics: Analgesia, anesthetic and sympathomimetic effects of ketamine are mediated by different sites of action. Non-competitive NMDA receptor antagonism is associated with the analgesic effects; opiate receptors may contribute to analgesia and dysphoric reactions; and sympathomimetic properties may result from enhanced central and peripheral monoaminergic transmission. Ketamine blocks dopamine uptake and therefore elevates synaptic dopamine levels. Inhibition of central and peripheral cholinergic transmission could contribute to induction of the anesthetic state.

Molecular Interaction / Receptor Chemistry: Cytochrome P450 3A4 is the principal enzyme responsible for ketamine N-demethylation to norketamine, with minor contributions from CYP2B6 and CYP2C9 isoforms. Potential inhibitors of these isoenzymes could decrease the rate of ketamine elimination if administered concurrently, while potential inducers could increase the rate of elimination

Psychological Effects: Decreased awareness of general environment, sedation, dream-like state, vivid dreams, feelings of invulnerability, increased distractibility, disorientation, and subjects are generally uncommunicative. Hallucinations, impaired thought processes, delirium, out-of-body experiences, and changes in perception about body, surroundings, time and sounds can occur at higher doses. Delirium and hallucinations can be experienced after awakening from full anesthetic doses of ketamine.

Physiological: Anesthesia, cataplexy, immobility, tachycardia, increased blood pressure, nystagmus, hypersalivation, increased urinary output, profound insensitivity to pain, amnesia, slurred speech, and lack of coordination.

Cardiovascular: Cardiovascular side effects have included elevated blood pressure and pulse rate following administration of ketamine alone. However, hypotension and bradycardia have been observed. Arrhythmia has also been reported.

Respiratory: Respiratory side effects have included stimulated respiration, although severe depression of respiration or apnea may occur following rapid intravenous administration of ketamine. Laryngospasms and other forms of airway obstruction have occurred during ketamine anesthesia.

Ocular: Ocular side effects have included diplopia, nystagmus, and a slight elevation in intraocular pressure.

Oral: Hypersalivation can occur but is rare.

Gastrointestinal: Gastrointestinal side effects have included anorexia, nausea, and vomiting.

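### The infusion time is limited only from above, so very rapid delivery complies although the protocol warns of apnea after rapid intravenous ketamine

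*Combined protocol and SAP*

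**What the plan says.** All of the dosing rules are in the Intervention Administration section of the combined protocol and SAP.

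- Dose: the pharmacy prepares "Ketamine bolus doses of 0.4 mg/kg (by ideal body weight"), and the section repeats that the dose is fixed.
- Route: "Ketamine will be given via intravenous infusion through an IV line established in the PACU".
- Time: "The study drug or control will be administered over <60 minutes".
- General clause: "The study drug will be administered in accordance to best practices".

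Overall study design and plan adds that patients, "if deemed medically stable by the study physician, will receive either 0.4mg/kg IV ketamine or placebo". The same section states: "There is no restriction on the use of other analgesics throughout the hospital stay".

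Two other statements bear on speed of delivery. The respiratory paragraph of the drug profile warns that "severe depression of respiration or apnea may occur following rapid intravenous administration of ketamine". The Background describes bariatric patients as a group "many of whom already suffer from respiratory compromise due to obesity and obstructive sleep apnea".

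Two background statements give rates for usual practice. The Background describes low-dose ketamine below 0.5 mg/kg/hr as routine and safe for inpatient pain. The drug profile gives 0.1 to 0.5 mg/kg/hr for analgesia, with a loading dose optional. Neither is written as a dosing rule for this trial.

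**The concern.** The one timing rule guards against slow delivery, while the protocol's own warning is about fast delivery. Speed is left to whoever gives the drug. That person is blinded, so cannot slow down on knowing that the syringe holds ketamine.

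At stake is the safety of patients who may have respiratory compromise and may be receiving opioids in the same hours. The secondary outcomes include opioid use in the PACU before and after the infusion, so the protocol expects that overlap. The best-practices clause contains no number. The stability check comes before dosing, and monitoring detects an event once it has begun. The side effects listed for monitoring in Intervention Administration include sedation but do not name respiratory depression or apnea.

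A smaller issue is uniformity of exposure. The 15-minute serum sample is timed from the end of the infusion, so it falls 10 + 15 = 25 minutes after the start of a 10-minute infusion but 59 + 15 = 74 minutes after the start of a 59-minute one.

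**Working it through.** The plan states no infusion rate, so there is no figure of its own to reproduce. The question is what the rule permits and how that compares with the rates the protocol describes.

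**Inputs.** Dose 0.4 mg/kg ideal body weight and time under 60 minutes (Intervention Administration). Reference rates: below 0.5 mg/kg/hr (Background) and 0.1 to 0.5 mg/kg/hr (drug profile). Lowest intravenous induction dose 1.0 mg/kg and half-life 2.3 ± 0.5 h (drug profile).

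**Step 1: permitted rates.** Rate (mg/kg/hr) = 0.4 × 60 / minutes = 24 / minutes.

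| Minutes | Rate (mg/kg/hr) | Multiple of 0.5 |
|---|---|---|
| 59 | 24/59 = 0.41 | 0.81 |
| 48 | 24/48 = 0.50 | 1.0 |
| 30 | 24/30 = 0.80 | 1.6 |
| 10 | 24/10 = 2.4 | 4.8 |
| 5 | 24/5 = 4.8 | 9.6 |

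All five rows comply with the timing rule.

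**Step 2: time needed to match the low-dose rate.** 0.4 / 0.5 × 60 = 48 minutes gives exactly 0.50. That is the top of the drug-profile range, but it does not meet the Background's strict limit of below 0.5. At 49 minutes the rate is 24/49 = 0.49, which meets both.

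**Step 3: sensitivity to the weight basis.** Neither reference rate says whether it is per kilogram of ideal or actual weight. If it is actual weight, and actual weight is 1.4 to 2.0 times ideal (an assumption), the trial dose is 0.4/1.4 = 0.29 to 0.4/2.0 = 0.20 mg/kg actual. The 48 minutes then becomes 48/1.4 = 34 to 48/2.0 = 24 minutes.

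**Step 4: effect on peak level.** In a one-compartment model with the same total dose, the level at the end of an infusion of length T is proportional to (1 − exp(−kT)) / (kT), with k = ln 2 / half-life. The ratio of the peak after 10 minutes to the peak after 59 minutes is 1.16 (half-life 1.8 h), 1.13 (2.3 h) and 1.10 (2.8 h). This takes the stated half-life as terminal and ignores the rapid distribution that the drug profile describes, so it is a lower bound.

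**Step 5: size of the respiratory risk.** The dose is 0.4/1.0 = 40% of the lowest induction dose. The apnea warning gives no dose and does not define rapid. No event rate and no threshold can be derived from the documents.

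**The case against.** The case for treating this as minor is substantial. The section repeatedly says infusion; *bolus* appears once, for the pharmacy preparation. A reader might infer that the protocol prescribes a push dose. It does not: infusion is the specified method, and the gap is that an infusion has no stated minimum length.

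The warning is one line of a general drug profile, and nothing shows that 10 or 30 minutes would count as rapid at this dose. Safeguards are layered: ASA status 1 to 3, exclusions for altered mental status, contraindication to ketamine and recent drugs that interfere with its metabolism, a physician's stability check, and dosing in a monitored PACU. These lower the practical risk, but none sets a time or rate.

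The 0.5 mg/kg/hr reference is also soft. The drug profile allows a loading dose, so faster initial delivery lies within the practice it describes, and the weight basis is unstated. A reader might infer that anything under 48 minutes is unsafe. The documents do not support that, and the fix should not be presented as resting on safety evidence.

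Finally, a rate may be set in an infusion order that is not part of these documents, and one figure near this section is not reproduced in the available text. If either states a minimum, the remaining task is to bring it into the dosing paragraph.

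**Conclusion.** The point holds as a gap in the dosing rule: delivery fast enough to meet the protocol's own warning complies with the protocol. A stated minimum time would close the gap at little cost, so this is a cheap improvement worth making.

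Its size is limited. The permitted rate runs from just above 24/60 = 0.40 mg/kg/hr with no upper bound, but the respiratory risk at 0.4 mg/kg ideal body weight cannot be sized from the documents. The gain in uniform exposure looks modest: the computed peak ratio of 1.10 to 1.16 is a lower bound under a simple model, and no effect on the questionnaire outcomes is shown. The comparison with 0.5 mg/kg/hr assumes the same weight basis.

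A reader might also infer that the loose rule biases the treatment comparison. It does not follow: the rule is the same in both arms and the administering staff are blinded.

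**What to change.** In Intervention Administration, delete *bolus* and replace the timing sentence with wording such as: *In both arms the study drug is given as a single pump-controlled infusion, target 50 to 55 minutes, not less than 49 and less than 60 minutes.* The target rates are 24/50 = 0.48 and 24/55 = 0.44 mg/kg/hr, with 24/49 = 0.49 at the minimum. All are below the Background's 0.5 on the same weight basis, and the existing upper limit stays.

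The investigators may choose a shorter minimum on clinical grounds. If they do, they should state it and not rely on the Background's low-dose statement to support it unless they also state the weight basis. The essential change is that a minimum exists.

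The cost is wording in one paragraph and in the infusion order. Dose, sample size and endpoints are unchanged. The downsides are less flexibility, a possibly longer infusion in the PACU, and some minor timing deviations when an infusion is paused or a line fails.
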